4.4.2 Data Collection and Follow-up for Withdrawn Subjects

Information collected before the participant withdraws consent can continue to be used; however, new information will not be collected.

5 Study Procedures

5.1 Visit 1

The subject will be identified for eligibility into the study. The study coordinator will consent and enroll the subject. For women of childbearing potential, a pregnancy test will be done if not done prior to surgery and it must be negative before you can continue in this study. Baseline data collected will include air leak status and surgical history.

5.2 Visit 2

Prior to their discharge from the hospital a member of the study team will review the instructions for completing the Patient Chest Tube Diary and will confirm that the standard clinical education for discharging with an indwelling chest tube and valve has been completed. For subjects randomized to Group 1 confirm that they have received their prescription for antibiotics. The antibiotic to be prescribed is cephalexin; it is the oral equivalent of the antibiotic used for perioperative coverage. In the event that the subject has an allergy to cephalexin or the cephalosporin group of antibiotics then clindamycin should be prescribed instead in following the typical perioperative coverage.

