4.4 Early Withdrawal of Subjects

4.4.1 When and How to Withdraw Subjects

Subjects may withdraw from the study at any time. Additionally, a subject may also be discontinued from the study, if, based on the judgment of the Investigator, it is in the best medical interests of the subject. Withdrawal initiated by the patient may be documented by written or oral withdrawal of the original informed consent, or the implicit withdrawal of consent reflected in patient noncompliance or the patient being lost to follow-up.

Subjects are considered "lost to follow-up" after 3 attempts to contact the participant. Study coordinators will document all attempts to contact subjects.

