For this study, the study treatment follow-up period is defined as the time of consent until 30 days following hospital discharge or until the removal of the chest tube if after 30 days.

Preexisting Condition

A preexisting condition is one that is present at the start of the study. A preexisting condition should be recorded as an adverse event if the frequency, intensity, or the character of the condition worsens during the study period.

General Physical Examination Findings

At screening, any clinically significant abnormality should be recorded as a preexisting condition. At the end of the study, any new clinically significant findings/abnormalities that meet the definition of an adverse event must also be recorded and documented as an adverse event.

Post-study Adverse Event

All unresolved adverse events should be followed by the sponsor-investigator until the events are resolved, the subject is lost to follow-up, or the adverse event is otherwise explained. At the last scheduled visit, the sponsor-investigator should instruct each subject to report, to the sponsor-investigator, any subsequent event(s) that the subject, or the subject's personal physician, believes might reasonably be related to participation in this study.

Abnormal Laboratory Values

A clinical laboratory abnormality should be documented as an adverse event if it requires active management or treatment.

Hospitalization, Prolonged Hospitalization or Surgery

Any adverse event that results in hospitalization or prolonged hospitalization should be documented and reported as a serious adverse event unless specifically instructed otherwise in this protocol. Any condition responsible for surgery should be documented as an adverse event if the condition meets the criteria for an adverse event.

Neither the condition, hospitalization, prolonged hospitalization, nor surgery are reported as an adverse event in the following circumstances:

 Hospitalization or prolonged hospitalization for diagnostic or elective surgical procedures for a preexisting condition. Surgery should **not** be reported as an outcome of an adverse event if the purpose of the surgery was elective or diagnostic and the outcome was uneventful.

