7.2 Recording of Adverse Events

At each contact with the subject, the study team must seek information on adverse events by specific questioning and, as appropriate, by examination. Information on all adverse events should be recorded immediately in the source document, and also in the appropriate adverse event section of the case report form (CRF). All clearly related signs, symptoms, and abnormal diagnostic, laboratory or procedure results should recorded in the source document.

Adverse event data related to the indwelling chest tube, valve, ongoing air leak, or antibiotic use (group one) occurring during the study period must be recorded. The clinical course of each event should be followed until resolution, stabilization, or until it has been ultimately determined that the study treatment or participation is not the probable cause. Serious adverse events that are still ongoing at the end of the study period must be followed up, to determine the final outcome. Any serious adverse event that occurs during the Adverse Event Reporting Period and is considered to be at least possibly related to the study treatment or study participation should be recorded and reported immediately.

CTCAE Version 5.0 (v5.0: November 27, 2017) will be used to standardize classification and grading of Adverse Events.

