8.1 Confidentiality

Information about study subjects will be kept confidential and managed according to the requirements of the Health Insurance Portability and Accountability Act of 1996 (HIPAA). Those regulations require a signed subject authorization informing the subject of the following:

- What protected health information (PHI) will be collected from subjects in this study
- · Who will have access to that information and why
- Who will use or disclose that information
- The rights of a research subject to revoke their authorization for use of their PHI.

In the event that a subject revokes authorization to collect or use PHI, the investigator, by regulation, retains the ability to use all information collected prior to the revocation of subject authorization. For subjects that have revoked authorization to collect or use PHI, attempts should be made to obtain permission to collect at least vital status (long term survival status that the subject is alive) at the end of their scheduled study period.

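### Section 4.4.2 stops data collection at withdrawal of consent while 7.1 and 7.2 require open adverse events to be followed, and subjects discontinued by the investigator have no data rule

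*Protocol*

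**What the plan says.** Five places in the protocol bear on what is collected after a subject leaves or is taken off.

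- **Section 4.4.2**, the only section headed for withdrawn subjects: "Information collected before the participant withdraws consent can continue to be used; however, new information will not be collected". It gives no exception for adverse events or endpoints.
- **Section 4.4.1** says that patient-initiated withdrawal may be documented by written or oral withdrawal, or by "the implicit withdrawal of consent reflected in patient noncompliance or the patient being lost to follow-up". It also provides that "a subject may also be discontinued from the study, if, based on the judgment of the Investigator", this serves the subject's medical interests.
- **Section 7.1**, under its heading for the time after the study, says: "All unresolved adverse events should be followed by the sponsor-investigator until the events are resolved, the subject is lost to follow-up". A third exit is that some other explanation has been found.
- **Section 7.2** has each event followed to resolution, stabilization or a finding that the study is not the probable cause. It adds: "Serious adverse events that are still ongoing at the end of the study period must be followed up, to determine the final outcome".
- **Section 8.1**, for subjects who revoke authorization to collect or use health information: "attempts should be made to obtain permission to collect at least vital status" at the end of the scheduled study period.

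Section 6.2 makes the primary analysis ITT on 30-day empyema, with the same approach for 30-day readmission. If 30-day follow-up is incomplete, it turns to Kaplan-Meier and Cox methods.

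**The concern.** A site with a withdrawn subject and an open adverse event has two instructions that point in opposite directions. A site with a subject whom the investigator has discontinued has no instruction on endpoint data at all.

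**Safety.** The pause rule in section 7.4.2 works only if the study learns of disability, grade 4 events or death that could be consistent with antibiotic use. If 4.4.2 is applied to a subject deemed to have withdrawn while an event is evolving, the outcome may never reach the DSMB.

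**Efficacy.** ITT needs outcomes for everyone randomised. Censoring at departure is sound only if departure is unrelated to the risk of empyema or readmission. Subjects who leave because of a complication, or are removed for medical reasons, are those for whom this is least assured. Only Group 1 has an antibiotic and scheduled calls to be noncompliant with; the diary is common to both arms. Loss through implied withdrawal can therefore differ by arm and be tied to treatment.

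**Working it through.** **1. The rules side by side**

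| Subject | 4.4.2 | 7.1 and 7.2 | 8.1 |
|---|---|---|---|
| Explicitly withdraws consent, event open | no new data | follow the event; withdrawal is not an exit | applies only if authorization is also revoked |
| Deemed withdrawn for noncompliance, event open | no new data | follow the event; no exit | not triggered |
| Deemed withdrawn as lost to follow-up, event open | no new data | 7.1 ends; 7.2 has no such exit | not triggered |
| Discontinued by the investigator, consent not withdrawn | not expressly covered | follow the event | not triggered |
| Revokes authorization | applies if consent is also withdrawn | no exit | seek new permission, vital status as a minimum |

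Rows 1 and 2 are direct conflicts. Row 2 is the sharper one, because the subject may never have asked to leave. Row 3 conflicts with 7.2 only. Row 4 is a gap: adverse events are covered by section 7, but nothing covers empyema and readmission. In row 5, collecting under new permission is compatible with not collecting without it, so 8.1 and 4.4.2 can both be followed.

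**2. Does 8.1 recover the endpoints?** The only item it names is vital status. The endpoints are empyema (section 3.4) and 30-day readmission (section 3.5). Asking for them is allowed but not prompted. Section 3.6 already takes hospital admissions from source documents and the medical record.

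**3. Is this a sample-size problem?** Inputs: two-sided alpha 0.05, 80% power, 50% reduction, 253 per arm, 10% drop-out and a target of 560, all from section 6.1. The control rate is assumed to be the 16.5% cited in section 1.2, since 6.1 states none. So p1 = 0.165, p2 = 0.0825 and the mean rate is 0.12375.

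n per arm = [1.96·√(2·0.12375·0.87625) + 0.8416·√(0.165·0.835 + 0.0825·0.9175)]² / 0.0825²
= (0.9128 + 0.3889)² / 0.006806 ≈ 249.

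The plan's 253 is reproduced to within 1.6%. For drop-out, 506/0.90 = 563 and 506 × 1.10 = 557; the stated 560 lies between them.

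With 280 randomised per arm, power = Φ[(0.0825·√n − 0.9128)/0.4620]:

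| Loss | n per arm | Power |
|---|---|---|
| 5% | 266 | 82.6% |
| 10% | 252 | 80.5% |
| 15% | 238 | 78.2% |
| 20% | 224 | 75.7% |

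The planned 10% loss is covered.

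**4. What could unknown outcomes do?** At 10% loss from all causes, 28 per arm have no outcome. Expected events among the other 252 are 252 × 0.165 = 41.6 and 252 × 0.0825 = 20.8. The risk difference over all 280 per arm, treated minus control, is:

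- no events among the missing: (20.8 − 41.6)/280 = −7.4 percentage points
- all missing treated and no missing control subjects have events: −7.4 + 28/280 = +2.6 points
- the reverse: −7.4 − 10.0 = −17.4 points

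These are outer bounds for all drop-out, not an expected bias and not the share due to these sections.

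**The case against.** The strongest reply is that the sections have different triggers and can mostly be read together.

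- **Section 8.1.** A reader might infer a three-way contradiction, with 8.1 limiting collection to vital status. The text does not support that. It sets a minimum, applies after revocation and works through fresh permission. Both 8.1 and 4.4.2 also allow earlier data to be used. What stands is that neither endpoint is named. The consent pages are not available here, so what subjects are asked is not fully visible.
- **Investigator discontinuation.** A reader might infer that 4.4.2 closes the file on a Group 1 subject removed for an antibiotic complication. It is worded only for withdrawn consent, so it does not. Section 7 keeps that subject's adverse events under follow-up, and the pause rule can still be informed. What stands is the missing rule for endpoint data.
- **Noncompliance.** Section 4.4.1 is permissive: it says how a patient's withdrawal may be documented, and a careful site might not treat missed doses as leaving. The wording still allows it to.
- **Size.** A reader might convert the allowance of 560 − 506 = 54 subjects into a count of missed empyemas. That is not supported. The allowance covers all causes, events before withdrawal are kept, partial follow-up is censored, and a permission request cannot reach subjects who are lost to contact.

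None of this removes the conflict between 4.4.2 and 7.1/7.2. Nor can it be left to the statistical analysis plan, because an analysis cannot recover data that sites were told not to collect.

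**Conclusion.** The concern holds as one conflict, one gap and one omission.

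- **Conflict:** 4.4.2 against 7.1 and 7.2, for a subject who has withdrawn or is deemed to have withdrawn consent with an adverse event open.
- **Gap:** no endpoint-data rule for subjects discontinued by the investigator, although the primary analysis is ITT.
- **Omission:** the 8.1 request does not name empyema or readmission.

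The number of outcomes or events lost through these sections cannot be derived from the protocol. On the assumed 16.5% control rate, the planned loss leaves power at about 80%. What is at stake is bias from departures linked to treatment or complications, and incomplete safety data. The correction is worth making because following the text as written can lose outcomes that are obtainable, and it costs little.

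**What to change.** Put one reconciled rule in 4.4.2 and cross-reference it from 4.4.1, 7.1, 7.2 and 8.1.

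1. Subjects discontinued by the investigator, or noncompliant with the antibiotic, calls or diary, who have not explicitly withdrawn consent stay in follow-up for 30-day empyema, 30-day readmission and adverse events. Noncompliance alone no longer counts as withdrawal of consent.
2. At explicit withdrawal of consent or revocation of authorization, ask permission to read 30-day empyema, readmission and the outcome of any open adverse event from the medical record, as well as vital status. Record the answer.
3. State that the follow-up of open adverse events in 7.1 and 7.2 applies to withdrawn subjects who permit it.

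The cost is protocol wording, a line in the consent form and one withdrawal item on the CRF. No visits are added and the sample size does not change. The small downside is that some subjects will decline.

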Reinersman and colleagues evaluated outcomes of patients discharging with an indwelling chest tube from a high volume referral center. At the institution all patients who are discharged with an indwelling chest tube receive standard education from our nursing staff as to dressing changes, changing the dressing when saturated, and noting daily output and changes in output. All patients are instructed on how to check the device for air leak. If they notice the leak has ceased, they are to call for the next available appointment to be seen in clinic for possible chest tube removal. Additionally, all patients receive a standard dismissal education pamphlet summarizing the care of the chest tube and Heimlich valve or mini-Atrium[®]. They found that the rate of empyema was 16.5%, using strict criteria, including all patients with a leukocytosis or fever and an undrained effusion on chest x-ray or CT scan. The rate of readmission with a chest tube in place was found to be 25%.

Reinersman and colleagues found male gender, a history of coronary artery disease and peripheral vascular disease were found to be predictors of empyema (15). Traditional predictors of air leak were analyzed including pleural adhesions, chronic obstructive pulmonary disease, upper, age, use of steroids and decreased body mass index (1-3). These traditional predictors did not contribute to risk of empyema and readmission in their study. The number of patients who were on immunosuppressive medications was too small to determine a difference. The presence of diabetes approached significance but was not a major predictor. Examining reoperative surgery as a surrogate for pleural adhesions also did not show a statistically significant difference in rate of empyema or readmission (p=0.2) (15).

As previously discussed, Brunelli et al. reported that the presence of an air leak greater than 7 days led to a higher rate of empyema compared to patients without air leak or with a shorter duration air leak (14). Reinersman et al. also revealed a temporal relation to number of days with air leak and chest tube related to risk of empyema. The overall number of days with chest tube in place was found to be a predictor of empyema, with an incremental increase per one day with chest tube (HR 1.2, p=0.006). Further, the presence of an air leak and chest tube for more than 14 days markedly increased the risk of empyema (HR 7.6, p=0.047) (15).

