4.2 Exclusion Criteria

- Pregnancy
- Allergy to cephalexin or clindamycin
- Special consideration should be taken in enrolling subjects with preexisting conditions that can be exacerbated by antibiotic use but are allowed at the discretion of the treating physician.

Considerations include but are not limited to:

- C. difficile
- Colitis
- Impaired renal function
- Hypersensitivities to cephalosporins, penicillins, or lincomycin
- Hepatic impairment
- Anticoagulation therapy
- Metformin usage
- Probenecid usage

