6.2 Statistical Methods

Descriptive Statistics

Descriptive statistics for baseline and clinical variables will be reported as number (percentage) for discrete variables and as mean (SD) or median (range) as appropriate for continuous variables. Baseline demographic and clinical variables will be reported by treatment group. These assessments will help identify potential confounding variables to be used as covariates in multiple variable models when examining the outcomes between treatment arms.

Handling of Missing Data

In the event that we have patients without complete follow-up survival analyses for the outcomes of 30 day empyema and 30 day readmission will be utilized to account for differential patient censoring.

Multiplicity

This study has two treatment arms being compared. No multiple comparison adjustments are planned.

Primary Hypothesis: Assess whether patients receiving antibiotics and twice weekly calls have reduced 30-day **empyema** rates post-discharge compared to patients on standard of care.

The primary analysis will be intention to treat (ITT). The proportion of patients having 30-day empyema in the two treatment arms will be estimated and reported along with a 95% confidence interval. The association of treatment arm with the rate will be assessed using a Chi square test. Additionally, logistic regression will be used to examine the treatment effect accounting for baseline covariates in which there is important imbalance between treatment arms. If not all patients having complete follow-up to 30 days post-discharge then these same analyses will be performed using survival methods, estimates of survival-free of empyema using Kaplan Meier methods and Cox models for the assessment of the association of treatment arm and the risk of empyema. The alpha level will be set at 0.05 for statistical significance.

Secondary Hypothesis 1: Assess whether patients receiving antibiotics and twice weekly calls have reduced 30-day **readmission** rates post-discharge compared to patients on standard of care.

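### The protocol does not specify baseline collection of the empyema predictors it cites, although its baseline table and adjusted models rely on such variables (minor)

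*Protocol*

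**What the plan says.** **What is to be collected.** Protocol 5.1 (Visit 1) says: "Baseline data collected will include air leak status and surgical history". The Schedule of Events ticks three things at Visit 1: consent, air leak status and surgical history. It has no row for demographics, comorbidity, medication or tube placement date. Section 3.6 names the diary as recorded directly on the CRF. The record-based items it names are laboratory results, the clinical significance of observations, and hospital admissions.

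**What the analysis uses.** Section 6.2: "Baseline demographic and clinical variables will be reported by treatment group". It goes on: "These assessments will help identify potential confounding variables to be used as covariates in multiple variable models". For the primary endpoint, after the chi-square test, "logistic regression will be used to examine the treatment effect accounting for baseline covariates in which there is important imbalance between treatment arms". The same is planned for readmission, and Cox models replace logistic regression if follow-up to 30 days is incomplete.

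**What the protocol says is prognostic.** Section 1.2, on the earlier cohort from a high-volume referral center: "male gender, a history of coronary artery disease and peripheral vascular disease were found to be predictors of empyema". Also: "The overall number of days with chest tube in place was found to be a predictor of empyema". On diabetes: "The presence of diabetes approached significance but was not a major predictor".

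**Which patients raise a safety question.** Section 4.2: "Special consideration should be taken in enrolling subjects with preexisting conditions that can be exacerbated by antibiotic use". Its examples include C. difficile, colitis, renal and hepatic impairment, anticoagulation, metformin and probenecid. Such patients may enter at the treating physician's discretion.

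**Balance by design.** Section 8.3 (Data Management) stratifies randomisation by enrolment site and by nothing else.

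**The concern.** The sections that say what is gathered and the section that says what is analysed do not meet. A statistical analysis plan can choose among covariates, but it cannot supply data that sites were never told to record. Each site enters its own data (8.3), so fields left unnamed may be completed unevenly between sites.

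Late repair is also limited. Section 4.4.2 stops the collection of new information after withdrawal, and 4.4.1 treats loss to follow-up as an implicit withdrawal. On a plain reading, a history item not recorded at entry could not be added later for these patients, although they stay in the intention-to-treat set. The plan allows for 560 − 506 = 54 of them.

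At stake are the completeness of the baseline table, the usefulness of the adjusted models for both endpoints, and the ability to describe antibiotic harms in patients who had a condition of the kind listed in 4.2.

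**Working it through.** **Step 1. Does anything numerical depend on this?** Section 6.1 gives 253 per arm for a 50% reduction at two-sided alpha 0.05 and 80% power. It states no control rate; I assume the 16.5% empyema rate from 1.2, so p1 = 0.165, p2 = 0.0825 and their mean p = 0.12375.

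n per arm = [1.960·√(2p(1−p)) + 0.842·√(p1(1−p1) + p2(1−p2))]² / (p1 − p2)²

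= [1.960·√0.21687 + 0.842·√0.21347]² / 0.0825² ≈ 1.694 / 0.006806 ≈ 249.

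The stated 253 is within 3% of this and gives 80.6% power. For dropout, 506 × 1.10 = 557 and 506 / 0.90 = 563; the stated 560 lies between them. The sizing is therefore that of an unadjusted comparison of two proportions. No covariate enters it, and the fix changes neither 506 nor 560.

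**Step 2. Set the lists side by side.**

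| Variable | Why the protocol makes it relevant | Named in 5.1 or the Schedule | Named in 3.6 |
|---|---|---|---|
| Sex | Predictor (1.2) | No | No |
| Coronary artery disease | Predictor (1.2) | No | No |
| Peripheral vascular disease | Predictor (1.2) | No | No |
| Diabetes | Near-significant (1.2) | No | No |
| Tube days at discharge | Related to a predictor (1.2) | No; a surgery date may allow inference | No |
| Age | A demographic (6.2) | No | No |
| 4.2 conditions and medications | Possible antibiotic harm (4.2) | No | In part, through laboratory results |

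**Step 3. Which tube days?** The 1.2 result concerns the overall number of days with the tube. That total runs past randomisation and could itself be changed by closer monitoring, so it is not a baseline covariate. Days elapsed at discharge, when the assigned care starts, are usable. Section 4.1 asks for a consultation with a thoracic surgeon rather than an operation, so surgical history need not date the tube for every patient. Sections 2 and 5.1 do describe a surgical population, so it probably would for most.

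**Step 4. Can the model carry the cited predictors?** At the assumed rates, expected events are 253 × (0.165 + 0.0825) = 62.6. Treatment plus sex, coronary disease, peripheral vascular disease and tube days at discharge make five parameters: 62.6 / 5 ≈ 12.5 events per parameter. A short fixed list is feasible.

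**The case against.** The strongest reply is that the protocol does not rule these data out.

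- Section 5.1 uses open wording about what baseline data include.
- The Schedule is plainly not a full data list. It also omits the pregnancy test that 5.1 requires, randomisation, and the assessment of empyema and readmission.
- Section 6.2 commits to reporting demographics, so it presupposes that someone records them.
- Section 7.1 (General Physical Examination Findings) has clinically significant abnormalities at screening recorded as preexisting conditions.
- Sections 3.6 and 8.2 name the medical record as a source, and 4.3 lets routine results serve as study data.
- The CRF is not shown, and field lists and covariate lists often sit in the CRF and the analysis plan.

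Most of this stands. A reader might infer that the predictors will go unrecorded, that the adjusted models will be unable to include them, or that an imbalance in sex would go unseen. The documents do not support any of these.

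What the reply does not remove is the mismatch. The 4.3 provision is a permission and concerns tests rather than history. The 7.1 sentence concerns findings at screening and names no diagnosis. The commitment in 6.2 has no counterpart in any section on data collection.

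It may also be said that fixing covariates is a separate preference, because 6.2 adjusts for imbalance rather than for precision. That is a fair description of the plan. But in a randomised trial, imbalance arises by chance and is known only once the data are seen. Choosing covariates by known prognostic value is the better rule, and the protocol already holds the evidence for it.

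**Conclusion.** The point holds as a minor one. The protocol names predictors of empyema and plans analyses on baseline demographic and clinical variables, but does not specify that those predictors be collected. The supportive adjusted analyses of both endpoints and the description of harms by 4.2 condition are exposed. The primary intention-to-treat chi-square test and the sample size are not.

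A reader might go further and compound the hazard ratio of 1.2 per day in 1.2 over several days, or take the 7.6 cited for leak and tube beyond 14 days, and conclude that tube duration could swamp the halving the trial is sized to detect. The documents do not support this. Both ratios compare individual patients, and neither is stated for days before discharge. The treatment effect compares arms, whose averages randomisation balances in expectation. As an illustration, assume a standard deviation of 3 to 7 days at discharge (not in the documents). A 1.96-standard-error imbalance with 253 per arm is 1.96 × SD × √(2/253), or about 0.5 to 1.2 days. Even if 1.2 per day applied before discharge, that is a shift of about 1.10 to 1.25-fold. No effect on the primary result is claimed here.

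The conclusion rests on 5.1, the Schedule and 3.6 being where the protocol states what is collected, with the CRF unseen. A CRF that already carries these fields would reduce the collection part to a wording correction.

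**What to change.** **Collection.** In 5.1 and the Schedule of Events (Visit 1, both arms), list for abstraction from the chart: age, sex, coronary artery disease, peripheral vascular disease, diabetes, date of chest tube placement, and the special-consideration conditions and medications of 4.2.

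**Analysis.** In 6.2, name sex, coronary artery disease, peripheral vascular disease and tube days elapsed at discharge as pre-specified covariates in the adjusted logistic and Cox models, replacing selection by observed imbalance. State that total tube days will not be used as a covariate, because they accrue after randomisation.

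**Cost.** A few extra CRF fields per patient at a visit that already takes place, with slight data entry. There is no added procedure or patient contact, and no change to the primary test or the target of 560.
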